6.7 Treating the patient

Study drug administration

Everolimus is an oral drug to be self-administered by the patient with or without food and preferably around the same time every day.

Pasireotide is parenterally administered. The long acting formulation of Pasireotide will be administered intramuscularly by trained Oncology nurse at the beginning of each cycle. All dosages prescribed and dispensed to the patient and all dose changes during the study must be recorded.

The investigational study drugs used in the course of this trial are pasireotide (SOM230) and everolimus (RAD001). Novartis will supply pasireotide and everolimus free of charge for study participants.

Permitted study drug adjustments

Toxicity will be assessed using the NCI-CTC for Adverse Events, version 4.0 (CTCAEv4.0, (http://ctep.cancer.gov/protocoldevelopment/electronic_applications/docs/ctcaev4.pdf)). For patients who are unable to tolerate the protocol-specified SOM230C and RAD001 dosing schedule, dose-adjustment guidelines are given below.

The following dose modification schedules will be used where dose adjustment is necessitated by treatment related adverse events. The listed starting dose of Pasireotide may change if the ongoing phase I study established that higher doses of Pasireotide can be safely combined with the established dose of Everolimus.

Table Error! No text of specified style in document.6-2 SOM230C + RAD001 Dose Levels

Pasireotide LAR	
Dose level	Dose and schedule
0 (starting dose)	60 mg i.m. Q 4 weeks
Decrease 1 dose level	40 mg i.m. Q 4weeks
Decrease 2 dose levels	20 mg i.m. Q 4 weeks
Everolimus	
Dose level	Dose and schedule
0 (starting dose)	10 mg daily day 1 - 28

Decrease 1 dose levels	5 mg daily day 1 - 28
Decrease 2 dose levels	5 mg daily days 1 - 21 of a 28-day cycle
Decrease 3 dose levels	5 mg every other day for a 28-day cycle

Table 6-3-Criteria for dose-modification in case of suspected SOM230 and RAD001 toxicity for non-hematologic toxicity

Toxicity	Actions
Grade 2 (except pneumonitis [refer to Table 6-5] and mucositis)	If the toxicity is tolerable to the patient, maintain the same dose. If the toxicity is intolerable to patient, interrupt RAD001 and pasireotide until recovery to grade ≤ 1 . Then reintroduce RAD001 and pasireotide at one lower dose level.

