Grade 2 mucositis	If the toxicity is tolerable to the patient, maintain the same dose. If the toxicity is intolerable to patient, interrupt RAD001 and pasireotide until recovery to grade ≤ 1 . Then reintroduce RAD001 and pasireotide at one lower dose level. See Management of stomatitis/oral Mucositis/mouth ulcers for further details.
Grade 3 (except hyperlipidemia and hyperglycemia and mucositis and pneumonitis)	Interrupt RAD001 and pasireotide until recovery to grade ≤ 1 . Then reintroduce RAD001 and pasireotide at one lower dose level. If the same toxicity recurs at CTC grade ≥ 3 SOM230 and RAD001 will be discontinued.
Grade 3 hyperlipidemia	Grade 3 hyperlipidemia (hypercholesterolemia and/or hypertriglyceridemia) should be managed using medical therapies, see Management Guidelines for Hyperlipidemia and Hyperglycemia. Dose reduction of RAD001 and pasireotide can be considered but is not required.
Grade 3 hyperglycemia	Grade 3 hyperglycemia should be managed using medical therapies, see Management Guidelines for Hyperlipidemia and Hyperglycemia. Dose reduction of RAD001 or pasireotide can be considered but is not required.
Grade 3 mucositis	For Grade 3 mucositis, interrupt RAD001 until recovery to grade ≤ 1 . Then reintroduce RAD001 and pasireotide at one lower dose level See Management of stomatitis/oral Mucositis/mouth ulcers for further details.
Grade 3 pneumonitis	Please refer to Table 6-5
Grade 4	Discontinue pasireotide and RAD001.

Any non-hematological toxicity requiring interruption for > 3 weeks	Discontinue pasireotide and RAD001.
---------------------------------------------------------------------	-------------------------------------

Table 6-4 Criteria for dose-modification in case of suspected SOM230 and RAD001 for hematologic toxicity

Toxicity	Actions
Hematological toxicity	
Grade 2 Thrombocytopenia (platelets $<75, \geq 50 \times 10^9/L$)	Interrupt RAD001 until recovery to grade ≤ 1 ($>75 \times 10^9/L$). Then reintroduce RAD001 at initial dose. If thrombocytopenia again returns to grade 2, interrupt RAD001 until recovery to grade ≤ 1 . Then reintroduce RAD001 at the lower dose level.
Grade 3 Thrombocytopenia (platelets $<50, \geq 25 \times 10^9/L$)	Interrupt RAD001 until recovery to grade ≤ 1 (platelets $\geq 75 \times 10^9/L$). Then resume RAD001 at one dose level lower. If grade 3 thrombocytopenia recurs, discontinue RAD001.
Grade 4 Thrombocytopenia (platelets $< 25 \times 10^9/L$)	Discontinue RAD001.

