*Grade ≥ 3 and judged as at least possibly drug related	
 · Further injections should be held for at least 7 days and until toxicity improves to \leq Grade 1. · If toxicity improves to grade ≤ 1 within 7 days, no dose reduction is required. · If toxicity improves to grade ≤ 1 in 8-14 days, resume treatment with a single dose level reduction. · If toxicity improves to grade ≤ 1 in 15-28 days, resume treatment with two dose level reductions. · If toxicity fails to improve to grade ≤ 1 within 28 days, study treatment must be discontinued unless there is clear evidence of therapeutic benefit from the study regimen, in which case continued treatment is left to the discretion of the Overall Principal Investigator. · If any toxicity recurs at CTCAE grade ≥ 3, treatment must be discontinued.
QTc CTC grade 1 (≤ 480 msec)	
 · No study drug adjustments
QTc CTC grade 2 (> 480 or ≤ 500 msec) either drug related or drug unrelated	Patient is to be referred to a cardiologist for evaluation and appropriate management, and the patient can remain in the study 
 · Patient's study drug dose will be reduced to 1 dose level down
QTc CTC grade ≥ 3 (> 500 msec)	Discontinue study drug Follow patient for safety ^A

SOM230 Management Guidelines for Suspected Hepatic Toxicity

In case of suspected SOM230-related hepatic injury manifesting as abnormal LFTs, the following steps should be followed within 72 hours of awareness of abnormal liver function tests:

- Liver-directed medical history and physical examination (i.e. assess occupational hazards, concomitant medications including OTC meds, intercurrent illness, etc)
- Liver chemistry tests: ALT, AST, total bilirubin, (fractionate to direct/indirect bilirubin if total bilirubin is $> 2.0x$ ULN), Alb, PT (INR), ALP, and GGT
- Hepatitis screen:
 - anti-HAV, IgM (to confirm acute hepatitis A)
 - HbsAg, Anti-HBc
 - anti-HCV (if positive, PCR viral load should be assessed),
 - Anti-HEV
 - ANA antibodies, anti-smooth muscle anti-bodies, CMV, EBV
- Perform abdominal ultrasound (liver and biliary tree)

Liver chemistry tests should be monitored every 3-4 days until resolution or return to baseline status.

- For ALT or AST $> 5x$ ULN and $\leq 8x$ ULN:
 - Study medication should be temporarily interrupted and liver chemistry tests monitored every 3-4 days until resolution or return to baseline

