 - If resolution or return to baseline does not occur after 2 weeks, the patient should be discontinued.
 - If ALT or AST returns to less than $5x$ ULN, study drug can be resumed and patient can continue study per protocol
 - If ALT or AST rises above $5x$ ULN anytime after study drug is resumed, then study drug should be discontinued immediately.

Follow-up LFT monitoring will take place at 3-4 day intervals (Table 2).

[figure not shown]
SOM230 Hepatic-related discontinuation criteria

Study medication should be discontinued immediately if any of the discontinuation criteria below are met:

- ALT or AST $> 3x$ ULN and Total Bilirubin $> 2x$ ULN and ALP $< 2x$ ULN
- ALT or AST $> 5x$ ULN and $\leq 8x$ ULN persistent for more than 2 weeks
- ALT or AST $> 8x$ ULN

Re-challenge of study medication is prohibited once discontinuation criteria are met.

SOM230 LFT Management Algorithm

Follow-up for toxicities

Patients who interrupt or permanently discontinue SOM230 and RAD001 due to an adverse event or abnormal laboratory value should be followed at least weekly for 28 days after the last dose of SOM230 and RAD001, and subsequently at monthly intervals until resolution or stabilization of the event, whichever comes first. If a patient requires a SOM230 and RAD001 dose delay of > 21 days from the intended day of the next scheduled dose, then the patient should be discontinued from the study.

All patients will be followed for adverse events and serious adverse events for 28 days following the last dose of SOM230 and RAD001.

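### Table 6-3 does not except events that meet the pasireotide hepatic discontinuation criteria, so it can restart a drug that the liver section bars from re-challenge

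*Combined protocol and SAP*

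**What the plan says.** Section 6.7 holds two sets of dosing rules that reach the same liver event.

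The general rule is Table 6-3, whose title gives its scope: "Table 6-3-Criteria for dose-modification in case of suspected SOM230 and RAD001 toxicity for non-hematologic toxicity". A liver enzyme rise is a non-hematologic toxicity. The grade 3 row lists its exceptions: "Grade 3 (except hyperlipidemia and hyperglycemia and mucositis and pneumonitis". For any other grade 3 event both drugs are held until grade 1 or less. The row goes on: "Then reintroduce RAD001 and pasireotide at one lower dose level. If the same toxicity recurs at CTC grade" 3 or above, both are stopped. The grade 2 row excepts only pneumonitis and mucositis. Its first instruction is "If the toxicity is tolerable to the patient, maintain the same dose"; an intolerable grade 2 event leads to a hold and a restart one level lower. Grade 4, or an interruption of more than 3 weeks, means discontinuation. In Table 6-2 the pasireotide level below the 60 mg start is "40 mg i.m. Q 4weeks".

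The specific rule is the SOM230 hepatic guidance later in the section. It applies "In case of suspected SOM230-related hepatic injury manifesting as abnormal LFTs". Its action is "Study medication should be discontinued immediately if any of the discontinuation criteria below are met". The three criteria are:

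- ALT or AST above 3x ULN with total bilirubin above 2x and ALP below 2x ULN
- ALT or AST above 5x and up to 8x ULN for more than 2 weeks
- ALT or AST above 8x ULN

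It then closes the door: "Re-challenge of study medication is prohibited once discontinuation criteria are met".

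Neither set refers to the other. The algorithm figure under the liver guidance is not shown in the text available for this review.

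**The concern.** Table 6-3 names the events to which it does not apply and sends the reader elsewhere for pneumonitis, mucositis, hyperlipidemia and hyperglycemia. It gives no such pointer for liver events. A coordinator who opens Table 6-3 for a grade 3 transaminase rise finds a complete instruction, and it ends in another injection.

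Liver abnormalities are foreseeable. Section 1.3 reports occasional, transient liver test changes at higher pasireotide doses, and the footnotes to Table 7-1 require extra liver tests around the first injections. Pasireotide LAR is a depot given every 4 weeks, so a dose given in error cannot be taken back. What is at stake is the safety of individual patients and the consistency of sites, not the trial's efficacy inference.

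A second gap follows from the first. The re-challenge ban stands under a SOM230 heading but speaks of study medication, which is not defined there. In Arms C, A1 and B1 a site cannot tell whether everolimus must stop as well.

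**Working it through.** No formula applies. The check sets the two rules side by side, event by event, and reads off the pasireotide dose that each gives.

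**Inputs.** Dose levels of 60, 40 and 20 mg every 4 weeks (Table 6-2). Actions by grade and the 3-week limit on interruption (Table 6-3). The hepatic criteria and the re-challenge ban (section 6.7, SOM230 hepatic guidance). CTCAE v4.0 as the grading scale (section 6.7); its ALT, AST and bilirubin cut-offs are not printed.

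**Comparison for a patient at 60 mg**, assuming recovery to grade 1 or less within 3 weeks where Table 6-3 calls for a hold:

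| Event, suspected pasireotide-related | Grade | Table 6-3 | Liver section | Result |
|---|---|---|---|---|
| ALT or AST above 8x ULN | 3 | 40 mg | none | conflict |
| ALT or AST above 8x ULN | 4 | none | none | agree |
| ALT or AST above 3x, bilirubin above 2x, ALP below 2x ULN | 2, tolerable | 60 mg | none | conflict |
| same | 2, intolerable | 40 mg | none | conflict |
| same | 3 | 40 mg | none | conflict |
| same | 4 | none | none | agree |

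For a patient already at 40 mg the grade 3 conflict is 20 mg against none. At 20 mg there is no lower level, and section 6.9 discontinues after two reductions, so for grade 3 events the rules agree.

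**Dependence on the grade cut-off.** Let grade 3 for ALT or AST end at U times ULN. The main conflict covers values above 8x and up to U x ULN. As an illustration only, U = 20 gives a band from above 8x to 20x ULN. The band vanishes if U is 8 or less. The documents do not give U.

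**Can recovery come in time?** The follow-up rule in section 6.7 counts a pasireotide delay from the day the next dose was due. A rise found at the Day 22 liver test precedes the Day 29 injection by 29 − 22 = 7 days. With the 21-day allowance, recovery could take up to 7 + 21 = 28 days from detection before that rule ends treatment. The restart in Table 6-3 is therefore reachable, though not assured.

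**The 5x to 8x criterion.** Persistence beyond 2 weeks stops the drug under the liver section, while Table 6-3 waits until interruption exceeds 3 weeks. With injections 4 weeks apart, this one-week difference would seldom change a dose. It carries little weight here.

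**The case against.** The best reply is that the specific rule governs. The liver section is narrower, stricter and worded as a prohibition. The exception list in Table 6-3 is plainly not complete: QTc prolongation of grade 3 or more (Table 6-8a) and hepatitis C reactivation, recorded as grade 3 (Table 6-8), also require discontinuation, and Table 6-3 names neither. Section 6.9 lets an investigator withdraw a patient at any time for an adverse event or an abnormal laboratory value, so a site that obeys the ban has cover in the protocol. The Day 22 and Day 50 liver tests must be assessed before the second and third injections. All of this stands, and it makes a wrongful restart less likely. It does not supply a rule of precedence: the reader must infer it, while Table 6-3 as written re-doses a patient whom the liver section excludes.

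Section 6.9 is weak support for the conflict. It sends toxicity of grade 3 or higher to dose adjustment although Table 6-3 discontinues at grade 4, so it cannot be a literal override of specific provisions. The missing algorithm figure may also address precedence; the finding is limited to readable text.

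A reader might infer three stronger points. One is that the omission shows an intention to re-challenge. The omitted QT and hepatitis C rules point rather to a table that was not reconciled with later sections. Another is that every ALT or AST value above 8x ULN is in conflict, but at grade 4 both rules stop the drug. The third is that the ban also contradicts Table 6-3 for everolimus. The documents do not define study medication under the SOM230 heading, so that is an ambiguity and not a shown contradiction.

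**Conclusion.** Wrong as written: two safety rules in one section give opposite instructions for the same event. For a suspected pasireotide-related ALT or AST rise above 8x ULN at grade 3, the difference for a patient at the starting dose is 40 mg every 4 weeks against no further pasireotide. The criterion that combines ALT or AST, bilirubin and ALP conflicts likewise at grades 2 and 3.

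The main case assumes that grade 3 extends above 8x ULN. The combined criterion assumes that such an event can be graded below 4. Restarts after a hold also assume recovery to grade 1 or less within 3 weeks. The absence of a precedence rule is established only for the text that can be read.

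The consequence is probably infrequent. Section 1.3 calls liver test abnormalities occasional, but the documents give no rate, so no number of affected patients is claimed. No endpoint and no sample size figure depends on this point. It should be fixed because the remedy is nearly free and the possible error is a depot injection that the protocol itself forbids.

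**What to change.** Add one sentence to the grade 2 and grade 3 rows of Table 6-3 and to section 6.9, for example: *If any SOM230 hepatic-related discontinuation criterion is met, pasireotide is permanently discontinued and not re-challenged, regardless of CTCAE grade; this overrides Table 6-3.* The same sentence should state whether study medication includes everolimus in Arms C, A1 and B1.

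Keep the override that narrow. Excepting every ALT, AST or bilirubin elevation from Table 6-3 would leave an isolated bilirubin rise, ALT or AST at or below 5x ULN without the bilirubin criterion, and everolimus-attributed liver events with no dose rule in the readable text. It would also let a 5x to 8x event resume below 5x ULN with no stated reduction. Table 6-3 should continue to apply to all of these.

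The cost is protocol wording in the next amendment. Design, sample size and data collection do not change.

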6.8 Other concomitant medications

Concomitant therapy

Patients will be instructed not to take any additional medications (including over-the-counter products) during the course of the study without prior consultation with the investigator. At each visit, the investigator will ask the patient about any new medications he/she is or has taken after the start of the study drug.

All Concomitant medications/Significant non-drug therapies taken \leq 30 days prior to start and after start of study drug, including physical therapy and blood transfusions, should be recorded.

The following restrictions apply during the entire duration of the study:

- No other investigational therapy should be given to patients.
- No anticancer agents other than the study medication should be given to patients. If such agents are required for a patient then the patient must first be withdrawn from the study.
- Co-administration with strong inhibitors of CYP3A4 (e.g., ketoconazole, itraconazole, ritonavir) or P-glycoprotein (PgP) should be avoided
- Seville orange, star fruit, grapefruit and their juices affect P450 and PgP activity. Concomitant use should be avoided
- Co-administration with moderate CYP3A4 inhibitors (e.g., erythromycin, fluconazole) or PgP inhibitors should be used with caution. If patient requires co-administration of moderate CYP3A4 inhibitors or PgP inhibitors, reduce the dose of RAD001 to 5 mg daily. Additional dose reductions to 5 mg every other day may be required to manage toxicities. If the inhibitor is discontinued the RAD001 dose should be returned to the dose used prior to initiation of the moderate CYP3A4/PgP inhibitor.
- Avoid the use of strong CYP3A4 inducers. If patient requires co-administration of strong CYP3A4 inducers (i.e., phenytoin, carbamazepine, rifampin, rifabutin, Phenobarbital, St. John's wort), **the patient should be monitored as per protocol and discontinued from study treatment if progression occurs.** An increase in the dose of RAD001 from 10 mg up to 20 mg daily should be considered, using 5 mg increments. Enzyme induction usually occurs within 7-10 days, therefore RAD001 dose should be increased to 15 mg daily, 7 days

after the start of the inducer therapy. If no safety concerns are seen within the next 7 days, the dose can be increased again to 20 mg daily. This dose of RAD001 is intended to achieve similar AUC to the range observed without inducers. However, there are no clinical data with this dose adjustment in patients receiving strong CYP3A4 inducers. If the strong inducer is discontinued the RAD001 dose should be returned to the dose used prior to initiation of the strong CYP3A4/PgP inducer.

- No chronic treatment with systemic steroids or another immunosuppressive agents (at a dose equivalent of greater than 20 mg prednisone per day) or other immunosuppressive agents). Topical or inhaled corticosteroids are allowed.
- RAD001 may affect the response to vaccinations making the response to the vaccination less effective. Live vaccines should be avoided while a patient is treated with RAD001.
- QT prolonging medication - the use of concomitant medications that might lead to QT prolongation is prohibited and requires the discontinuation of the patient prior to starting the respective QT prolonging medication.

Oral anticoagulants such as warfarin are CYP2C9 substrates and, as such, no interaction with RAD001 is expected. However, drug-drug interaction studies between macrolide antibiotics and warfarin have produced mixed outcomes and the disparity in these findings has led to the conclusion that multiple factors may alter the clearance of warfarin. The co-administration of RAD001 and oral anticoagulants is possible but should be subject to verification of coagulation (INR) once steady state is reached (after one week's treatment).

Examples are provided in [Table 6-9](#). A comprehensive list of cytochrome P450 isoenzymes and CYP3A4 inhibitors, inducers, and substrates can be found at <http://medicine.iupui.edu/flockhart>. This website is continually revised and should be checked frequently for updates.

Table 6-9 Examples of clinically relevant drug interaction: substrates, inducers and inhibitors of isoenzyme CYP3A.

Substrates (competitive inhibition)	
Antibiotics¹: clarithromycin* erythromycin telithromycin* Anti-arrhythmics: quinidine Benzodiazepines: alprazolam diazepam midazolam triazolam Immune Modulators: cyclosporine tacrolimus (FK506) HIV Protease Inhibitors: indinavir* ritonavir* saquinavir* Prokinetic: cisapride Antihistamines: astemizole chlorpheniramine ⁶¹	Calcium Channel Blockers: amlodipine diltiazem felodipine nifedipine nisoldipine nitrendipine verapamil HMG CoA Reductase Inhibitors²: atorvastatin cerivastatin lovastatin simvastatin Miscellaneous: aprepitant buspirone haloperidol methadone pimozone quinine sildenafil tamoxifen trazodone vincristine
Inducers	
Carbamazepine Phenobarbital Phenytoin* Rifabutin*	Rifampin* St John's wort Troglitazone
Inhibitors	
Amiodarone Cimetidine Clarithromycin Delaviridine Diltiazem Erythromycin Fluvoxamine* Grapefruit juice Sevilla orange	Indinavir Itraconazole* Ketoconazole* Voriconazole* Posaconazole* Mibefradil Nefazodone* Nelfinavir* Troleandomycin Verapamil

Based on: Ingelman-Sundberg M, Human drug metabolising cytochrome P450 enzymes: properties and polymorphisms, Naunyn Schmiedebergs Arch Pharmacol. 2004 Jan;369(1):89-104. and [http://www.medicine.iupui.edu/flockhart/clinlist.htm as of July 13, 2006]

* asterisk denotes strong inhibition/ induction

Please note:

- strong inhibitor implies that it can cause ≥ 5 -fold increase in AUC or $\geq 80\%$ decrease in clearance of sensitive CYP substrates
- moderate inhibitor implies that it can cause 2 to 5-fold increase in AUC values or 50-80% decrease in clearance of sensitive CYP substrates.

(Distinction is not always categorical as interaction can vary according to conditions).

1. Macrolide antibiotics: Azithromycin is not a CYP3A substrate. It may therefore be employed where

antibiotherapy with a macrolide is desirable in a patient being treated with RAD001

2. Statins: Atorvastatin and pravastatin may be associated with RAD001, since a PK interaction study has shown that there is no relevant PK interaction.
-

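### Section 6.8's fixed everolimus dose of 5 mg daily with a moderate inhibitor gives no reduction to a patient already lowered to 5 mg daily, and fluconazole's status differs between 6.7 and 6.8

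*Combined protocol and SAP*

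**What the plan says.** For a patient who needs a moderate CYP3A4 or PgP inhibitor, section 6.8 states: "If patient requires co-administration of moderate CYP3A4 inhibitors or PgP inhibitors, reduce the dose of RAD001 to 5 mg daily". It continues: "Additional dose reductions to 5 mg every other day may be required to manage toxicities". When the inhibitor stops: "If the inhibitor is discontinued the RAD001 dose should be returned to the dose used prior to initiation of the moderate CYP3A4/PgP inhibitor".

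Table 6-2 in section 6.7 sets the everolimus levels below the 10 mg starting dose:

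- one level down: "5 mg daily day 1 - 28"
- two levels down: "5 mg daily days 1 - 21 of a 28-day cycle"
- three levels down: "5 mg every other day for a 28-day cycle"

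These levels are for toxicity. Section 6.7 introduces them with: "The following dose modification schedules will be used where dose adjustment is necessitated by treatment related adverse events". Table 6-3 shows how a patient reaches the first reduced level after, for example, grade 3 mucositis: "Then reintroduce RAD001 and pasireotide at one lower dose level".

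Section 6.9 limits dose reductions for toxicity to two levels.

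On fluconazole, the stomatitis guidance in section 6.7 puts it with ketoconazole and itraconazole, to be avoided in every patient because these drugs strongly inhibit everolimus metabolism. Section 6.8 gives it as an example of a moderate inhibitor that may be given with caution. The inhibitor panel of Table 6-9 does not list it.

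**The concern.** The section 6.8 rule is a fixed target, not a step relative to the current dose. It works for a patient on 10 mg. A patient whom toxicity has already brought down to 5 mg daily meets the target before the inhibitor starts, so a site following the text need not change anything. The patients who have already shown intolerance of everolimus therefore get the least protection at the moment exposure is expected to rise. No other section sets a dose for a patient at or below 5 mg daily when an inhibitor is added.

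The fluconazole wording can meet this gap in one patient. Mouth toxicity is a usual reason for lowering everolimus, and a diagnosed fungal infection in such a patient raises the question of a systemic azole. Section 6.7 points one way and section 6.8 the other.

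What is at stake is the safety of patients taking everolimus: Arms A and C, and patients who move to the combination as A1 or B1.

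**Working it through.** The protocol gives no figure to reproduce here. The check compares the 6.8 target with each relevant dose level.

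**Inputs**

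- Dose levels: Table 6-2.
- Target with a moderate inhibitor: 5 mg daily (section 6.8).
- Inhibitor effect F: 2- to 5-fold AUC (notes to Table 6-9). The notes give this for sensitive CYP substrates, so using it for everolimus is an assumption.
- AUC proportional to dose: section 1.4 states this for 5 and 10 mg daily. Using it for every-other-day or 21-of-28-day dosing is an extrapolation.

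**Everolimus per 28-day cycle**

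- 10 mg daily: 10 × 28 = 280 mg
- 5 mg daily: 5 × 28 = 140 mg
- 5 mg on days 1 to 21: 5 × 21 = 105 mg
- 5 mg every other day: 5 × 14 = 70 mg

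**Dose change when the inhibitor starts, under section 6.8**

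- From 10 mg daily: 140/280 − 1 = −50%
- From 5 mg daily: 140/140 − 1 = 0%

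**Exposure relative to the patient's own earlier exposure** = (new total / old total) × F

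| Situation | F = 2 | F = 5 |
|---|---|---|
| 10 mg cut to 5 mg daily | 140 × 2/280 = 1.0 | 140 × 5/280 = 2.5 |
| 5 mg daily left unchanged | 140 × 2/140 = 2.0 | 140 × 5/140 = 5.0 |
| 5 mg daily to 5 mg on days 1–21 | 105 × 2/140 = 1.5 | 105 × 5/140 = 3.75 |
| 5 mg daily to 5 mg every other day | 70 × 2/140 = 1.0 | 70 × 5/140 = 2.5 |

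**Against the uninhibited 10 mg dose (280 mg)**

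- 5 mg daily left unchanged: 140 × 2/280 = 1.0 to 140 × 5/280 = 2.5
- 5 mg every other day: 70 × 2/280 = 0.5 to 70 × 5/280 = 1.25

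Moving one Table 6-2 level, from 5 mg daily to the 21-day schedule, cuts the total by only 25% (105/140 − 1) and leaves the dose on days 1 to 21 at 5 mg. Moving to 5 mg every other day is a 50% cut. It gives the reduced-dose patient the same relative protection, 1.0 to 2.5 times own exposure, that section 6.8 already gives a 10 mg patient.

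**If the inhibitor has no effect (F = 1)**: 70/140 = 0.5 times own exposure. This is the under-dosing risk of the change, in the same proportion as for a 10 mg patient under the present rule (140/280 = 0.5).

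**The case against.** The best defence is that the gap is narrow. Section 6.8 asks for caution, covers only patients who require the inhibitor, expects the investigator to be consulted before any new medicine, and already names 5 mg every other day as the next step. The toxicity tables still apply. Other text reduces how often the situation arises: topical antifungals are preferred, everolimus is stopped for invasive fungal infection, and a note to Table 6-9 offers azithromycin as a macrolide. On exposure, a patient left on 5 mg daily ends at 1.0 to 2.5 times the 10 mg level, the same absolute range that 6.8 accepts for a full-dose patient.

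Most of this stands as a limit on frequency. It does not close the gap. The every-other-day step is optional and comes after toxicity appears. The equal absolute range gives little comfort for someone already reduced because 10 mg was not tolerated.

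Several stronger readings are tempting but unsupported:

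- A reader might infer that 6.8 raises the dose of a patient already below 5 mg daily. The instruction is to reduce, so it cannot direct an increase. For these patients the text is silent.
- A reader might take the 2- to 5-fold range as a known everolimus effect. The documents give no everolimus-specific ratio for moderate inhibitors.
- A reader might see the fluconazole texts as irreconcilable. Avoiding it by default and reducing everolimus if it is required is a workable joint reading. The labels of strong and moderate do differ, and Table 6-9 does not settle which applies.
- A reader might infer that section 6.9 forbids the every-other-day dose because it is the third level down. The 6.9 limit concerns toxicity attributed to study drug, and 6.8 restores the earlier dose afterwards, which suggests a separate step. The text does not say so.

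**Conclusion.** The point holds as a safety-wording defect worth correcting. At inhibitor start, section 6.8 gives a 50% cut to a 10 mg patient and none to a patient on 5 mg daily. That follows directly from the text.

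The exposure figures (2 to 5 times own earlier exposure, 1.0 to 2.5 times that of 10 mg) are conditional. They rest on applying the Table 6-9 range to everolimus and on dose-proportional AUC, and are illustrative only. Few patients are likely to be affected. Their number cannot be derived, because the documents give neither a dose-reduction rate nor a rate of moderate-inhibitor use for this population.

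The fluconazole inconsistency is real but mainly one of classification. Nothing here bears on sample size, error rates or the response-rate decision rule.

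**What to change.** In section 6.8, replace the fixed target for moderate CYP3A4 or PgP inhibitors with:

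- From 10 mg daily, go to 5 mg daily.
- From 5 mg daily, go to 5 mg every other day when the inhibitor starts.
- Below 5 mg daily, never raise the dose to 5 mg daily. Prefer a non-interacting alternative; otherwise agree the dose or a hold with the overall PI.
- Keep the return to the earlier dose when the inhibitor stops, and state that this temporary step does not count toward the two-level toxicity limit in 6.9.

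A decision with the overall PI is better than a mandatory hold below 5 mg daily. Table 6-9 lists inhibitors such as diltiazem and verapamil that may be long-term treatment, and a forced hold could then end study therapy. Section 6.2 lists 2.5 mg tablets, so a lower dose is practicable.

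Give fluconazole one status in 6.7 and 6.8: avoid it by default, with topical agents first, and if a diagnosed infection makes it unavoidable, apply the 6.8 reduction above. Deleting it from 6.8 altogether would leave no named dose rule for that case.

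As a clerical item, exclusion 20 should cite Table 6-9 for CYP3A inhibitors, not Table 6-5, which covers pneumonitis.

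The cost is a few sentences in the next amendment, with no new procedures or patients. The downside is possible temporary under-dosing in a few patients, down to 0.5 times own exposure if the inhibitor has no effect.
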